8.7. SOFTWARE VERSION

Non-compartmental PK parameter calculations will be performed using Phoenix® WinNonlin® 6.4 or higher (Certara, Princeton, New Jersey). All other derivations, statistical analyses, summaries, listings and graphics will be generated using SAS® version 9.4 (SAS® Institute, Inc., Cary, North Carolina).

9. STATISTICAL CONSIDERATIONS

9.1. ADJUSTMENTS FOR COVARIATES TO BE INCLUDED IN ANALYSES

Due to the small size of the study, no adjustment for covariates will be made.

9.2. MULTICENTER STUDIES

This study will be conducted by multiple investigators at multiple centers internationally. Data from all sites will be pooled for analysis.

9.3. MISSING DATA

Missing safety data will not be imputed. Partial dates for safety data will be imputed as outlined in Appendix 2 of this analysis plan. Missing efficacy data will be handled as described in Section 17.1.2 of this analysis plan. Missing PK data will be handled as described in Section 18.2 of this analysis plan.

9.4. EXAMINATION OF SUBGROUPS

No subgroup analyses will be performed for this study.

9.5. MULTIPLICITY

No formal hypothesis testing will be performed; therefore, no multiplicity adjustment is required.

10. OUTPUT PRESENTATIONS

The templates provided with this SAP describe the presentations for this study and therefore the format and content of the summary tables, figures, and listings to be provided by Biostatistics. Appendix 1 describes the conventions for presentation of data in outputs. Minor modifications may be made to the tables, figures, and listings to accommodate the data.

11. DISPOSITION AND WITHDRAWALS

All subjects who provided informed consent (ENR) will be accounted for in this study. Subject disposition will be listed and summarized, including:

- Total subjects screened
- Number of screen failures (subjects who consent to participate in the clinical study but are not subsequently entered in the study)
- Total of subjects in the FAS
- Total subjects ongoing (subjects ongoing at the time of the IA)
- Total number of subjects in the SAF
- Total number of subjects in the PPS
- Total number of subjects in the PK Analysis Set
- Total subjects who discontinue from study treatment
- Total subjects who discontinue from the study
- Protocol deviations (PD) as obtained from the CTMS PD log

PDs will be identified and discussed with the Investigator/AnaptysBio in PD review meetings to categorize them, and to finalize analysis set assignment.

A subject is considered to have completed the study if they have completed all scheduled study visits

including the last visit on Day 169.

12. DEMOGRAPHIC AND OTHER BASELINE CHARACTERISTICS

Demographic data and other Baseline characteristics will be presented for the SAF. No statistical testing will be carried out for demographic or other Baseline characteristics.

The following demographic characteristics will be summarized and listed for this study:

- date of birth and age at informed consent
- gender
- height, weight and BMI; BMI $(kg/m^2) = weight (kg)/[height (m)]^2$
- ethnicity and race

If the date of birth is partial, age will be calculated using the available parts of the date.

Baseline characteristics will include Baseline values of efficacy and safety variables. Continuous variables will be summarized using count, mean, SD, median, minimum, and maximum. Categorical variables will be summarized using frequency and percentage.

13. MEDICAL HISTORY

Medical history will be captured on the MH eCRF at Screening and coded using the latest version of the Medical Dictionary for Regulatory Activities (MedDRA). Medical History will be provided in a listing. The duration of a smoker's smoking period will be calculated as follows:

Smoking period duration in years = date of informed consent - smoking start date

If the smoking start date is partial, only the available parts will be compared to the same parts of the date of informed consent.

Medical history for the SAF will be summarized and listed by System Organ Class (SOC), Preferred Term (PT), High Level Term and Lowest Level Term.

14. MEDICATIONS

Medications will be captured on the Prior and Concomitant Medications (CM) eCRF and coded using the latest version of the World Health Organisation (WHO) Drug Dictionary and Anatomical Therapeutic Chemical (ATC) system.

Prior and Concomitant medications will be identified as follows:

- 'Prior' medications are medications that stopped prior to the first dose of the study treatment.
- 'Concomitant' medications are medications which started prior to, on or after the first dose of study treatment, and continue after Day 1.

In the case where it is not possible to define a medication as prior or concomitant, the medication will be classified as the worst case i.e. concomitant. See APPENDIX 2 for handling of partial dates for medications. All prior, concomitant and rescue medications for the SAF will be listed and summarized by ATC Level 2 categories and preferred name.

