#### **9.4.3 Concomitant Medication**

All medications will be coded using the World Health Organization Drug Dictionary and Anatomical Therapeutic Chemical (ATC) system. Each medication will be classified as prior medication if it is stopped prior to the first dose of study drug, or as concomitant medication if it is ongoing at the time of the first dose or is started after the first dose of study drug. Prior, concomitant and rescue medications will be summarized by ATC level 2 categories and preferred name.

A listing of prior, concomitant, and rescue medications will be presented.

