APPENDIX 2. PARTIAL DATE CONVENTIONS

ALGORITHM FOR TREATMENT EMERGENT ADVERSE EVENTS

START DATE	STOP DATE	ACTION
Known	Known	If start date < study med start date, then not TEAE If start date >= study med start date, then TEAE
	Partial	If start date < study med start date, then not TEAE If start date >= study med start date, then TEAE
	Missing	If start date < study med start date, then not TEAE If start date >= study med start date, then TEAE
Partial, but known components show that it cannot be on or after study med start date	Known	Not TEAE
	Partial	Not TEAE
	Missing	Not TEAE
Partial, could be on or after study med start date	Known	If stop date < study med start date, then not TEAE If stop date >= study med start date, then TEAE
	Partial	Impute stop date as latest possible date (i.e. last day of month if day unknown or 31st December if day and month are unknown), then: If stop date < study med start date, then not TEAE

Page 40 of 43

START DATE	STOP DATE	ACTION
		If stop date >= study med start date, then TEAE
	Missing	Assumed TEAE
Missing	Known	If stop date < study med start date, then not TEAE If stop date >= study med start date, then TEAE
	Partial	Impute stop date as latest possible date (i.e. last day of month if day unknown or 31st December if day and month are unknown), then: If stop date < study med start date, then not TEAE If stop date >= study med start date, then TEAE
	Missing	Assumed TEAE

ALGORITHM FOR PRIOR/CONCOMITANT MEDICATIONS

START	STOP	ACTION
DATE	DATE	
Known	Known	If (stop date < study treatment start date), assign as prior
		If (stop date >= study treatment start date) and (start date <= end of
		treatment), assign as concomitant
		If (stop date >= study treatment start date) and (start date > end of
		treatment), assign as post treatment

START	STOP	ACTION
DATE	DATE	
	Partial	Impute stop date as latest possible date (i.e. last day of month if day unknown or 31st December if day and month are unknown), then: If (stop date < study med start date), assign as prior If (stop date >= study med start date) and (start date <= end of treatment), assign as concomitant If (stop date >= study med start date) and (start date > end of treatment), assign as post treatment
	Missing	If stop date is missing, medication can never be assumed as prior If (start date <= end of treatment), assign as concomitant If (start date > end of treatment), assign as post treatment

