Partial	Known	Impute start date as earliest possible date (i.e. first day of month if day unknown or 1st January if day and month are unknown), then: If (stop date < study med start date), assign as prior If (stop date >= study med start date) and (start date <= end of treatment), assign as concomitant If (stop date >= study med start date) and (start date > end of treatment), assign as post treatment
	Partial	Impute start date as earliest possible date (i.e. first day of month if day unknown or 1st January if day and month are unknown) and impute stop date as latest possible date (i.e. last day of month if day unknown or 31st December if day and month are unknown), then: If (stop date < study med start date), assign as prior If (stop date >= study med start date) and (start date <= end of treatment), assign as concomitant If (stop date >= study med start date) and (start date > end of treatment), assign as post treatment

Page 42 of 43

START	STOP	ACTION
DATE	DATE	
	Missing	Impute start date as earliest possible date (i.e. first day of month if day
		unknown or 1st January if day and month are unknown), then:
		If stop date is missing, medication can never be assumed as prior
		If (start date <= end of treatment), assign as concomitant
		If (start date > end of treatment), assign as post treatment
Missing	Known	If (stop date < study med start date), assign as prior
		If (stop date >= study med start date), assign as concomitant
		Cannot be assigned as 'post treatment'
	Partial	Impute stop date as latest possible date (i.e. last day of month if day
		unknown or 31st December if day and month are unknown), then:
		If (stop date < study med start date), assign as prior
		If (stop date >= study med start date), assign as concomitant
		Cannot be assigned as 'post treatment'
	Missing	Assign as concomitant

Statistical Analysis Plan

AnaptysBio Inc. PROTOCOL ANB019-002

Page 43 of 43

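### SAP Appendix 2 moves drugs started after an undefined end of treatment into a post-treatment class that protocol 9.4.3 and SAP 14 do not have and that no planned table summarises

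*SAP*

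**What the plan says.** **Protocol 9.4.3** has two timing classes. A drug is prior if it stopped before first dose. It is a "concomitant medication if it is ongoing at the time of the first dose or is started after the first dose of study drug". There is no later limit and no third class. Rescue medication is also summarised.

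**SAP 14** keeps the same two classes. Concomitant drugs are those that "started prior to, on or after the first dose of study treatment, and continue after Day 1", and a drug that cannot be classified defaults to concomitant. The planned output is: "All prior, concomitant and rescue medications for the SAF will be listed and summarized by ATC Level 2 categories and preferred name". The appendix is cited for one purpose only: "See APPENDIX 2 for handling of partial dates for medications".

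**SAP Appendix 2**, in the algorithm for prior and concomitant medications, adds a third outcome. With a known start and a missing stop date, the rule is "If (start date > end of treatment), assign as post treatment". The row for two complete dates has a matching branch, which begins "If (stop date >= study treatment start date) and (start date > end of" and ends in the same assignment. The rows for partial start dates repeat it. Only the rows for a missing start date rule the class out.

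**SAP 5.4** states that the analysis is unchanged from the protocol. **SAP 8.3** names end of treatment and end of study as separate terms, but no section gives a date for the first.

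**The concern.** Three texts classify the same drugs, and one disagrees with the other two. The disagreement is not confined to incomplete dates, which is all SAP 14 sends to the appendix, because the branch also acts when both dates are complete. The worst-case default in SAP 14 does not help, since the algorithm treats these drugs as classifiable.

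The new class has no summary. A programmer who follows the appendix would produce a concomitant-medication table that omits drugs the protocol says belong in it, and the SAP would not record the departure. The Schedule of Activities collects concomitant medication at every contact to Day 169, so the omitted drugs are ones the study sets out to record.

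The omission also breaks the match with adverse events. The treatment-emergent definition (protocol 9.4.5.1, SAP 19.1.1) and its date algorithm in Appendix 2 have a lower limit at first dose and no upper limit. An event after the last dose is summarised, while the drug given for it is not.

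**Working it through.** The documents give no figure to reproduce, so the check applies the three rules to the same drug and counts the start days on which they differ.

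**Inputs**
- First dose Day 1; last scheduled dose Day 85, visit window ±2 days (SAP 5.1, Table B).
- Week 16 visit Day 113 and end of study Day 169 (SAP Table B). Week 16 is a primary time point (SAP 3.1.1).
- Week 4 nonresponders are terminated four weeks after the intravenous dose (protocol 4.1), taken as Day 29 with no dose given that day.
- Assumption: end of treatment is the date of last dose. For a completer, the end of the 12-week treatment period falls at the same point.

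**One drug, three rules: a course from Day 100 to Day 107 in a completer**

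| Rule | Test | Class |
|---|---|---|
| Protocol 9.4.3 | started after first dose | concomitant |
| SAP 14 | started after first dose, continues past Day 1 | concomitant |
| SAP Appendix 2 | stop 107 ≥ 1 and start 100 > 85 | post treatment |

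An adverse event with onset on Day 100 is treatment-emergent, because 100 ≥ 1. For drugs started on or before Day 85 and continuing after Day 1, all three rules agree.

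**Start days reclassified in a completer**

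Days to end of study = 169 − last dose day. Days up to and including Week 16 = 113 − last dose day.

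| Last dose | To Day 169 | To Day 113 |
|---|---|---|
| Day 83 | 169 − 83 = 86 | 113 − 83 = 30 |
| Day 85 | 169 − 85 = 84 | 113 − 85 = 28 |
| Day 87 | 169 − 87 = 82 | 113 − 87 = 26 |

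**Week 4 nonresponder given only the Day 1 dose**

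The cut-off is Day 1, so start days 2 to 29 are affected: 29 − 1 = 28 days. This count needs the last-dose reading. If the cut-off were the end of the 12-week period, these drugs would stay concomitant.

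**Under protocol 9.4.3**

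No start day after first dose is reclassified in either case.

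**The case against.** The strongest reply is that little information is lost. Protocol 9.4 calls for by-subject listings of all data, and SAP Appendix 1 asks that every eCRF variable with data appear in the listings. With about 10 subjects, those listings are the practical tool for reviewing medication. Drugs flagged as rescue, including the topical corticosteroids named in protocol 6.5.1, are still summarised. Use of excluded therapy is a protocol violation and should surface among the deviations. A drug with a missing start date cannot enter the class, and a partial start date is imputed to the earliest possible day, which favours concomitant. All of this stands, and it limits the loss to non-rescue drugs in a summary table.

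It is also fair to say that nothing states whether SAP 14 or Appendix 2 prevails. The output templates mentioned in SAP 10 are not part of the text available, and they might include a post-treatment block. If end of treatment were read as end of study, the gap would nearly vanish, although SAP 8.3 separates the two terms. These points make the consequence conditional. They do not reconcile the texts.

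A reader might go further and infer that the branch hides confounding of the Week 16 response. The documents do not support that. Responder status, the missing-data rules and the denominator (SAP 17.1.1 to 17.1.3) make no use of medication class, and SAP 17.1.4 plans no sensitivity analysis that could use it. The planned table is by ATC level and preferred name with no time axis, so even a correctly classified Day 100 drug could not be placed before or after Week 16 from that table. Only the dated listings show this, and they are unaffected.

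**Conclusion.** The SAP is wrong as written on this point. Appendix 2 contradicts protocol 9.4.3 and SAP 14, uses a cut-off the SAP never defines, creates a class with no planned summary, and sits beside a statement that nothing has changed.

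The consequence is minor. If the appendix is followed and end of treatment means last dose, 82 to 86 start days in a completer, 26 to 30 of them on or before the Week 16 visit, leave the concomitant summary for non-rescue drugs. In a nonresponder given only the intravenous dose, the affected days are Days 2 to 29. These are calendar days on which a new drug would be misclassified. They should not be read as a share of medications, because the documents do not say how many drugs would start in those windows. The primary endpoint calculation does not change.

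**What to change.** Preferred: delete the post-treatment branch from every row of the medication algorithm in Appendix 2, so that a drug ongoing at first dose or started after it is concomitant, as in protocol 9.4.3. The medication table then covers the same period as the treatment-emergent adverse events.

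Alternative, if the sponsor wants the class: add it to SAP 14, define its cut-off date for completers and for subjects who stop early, plan a summary for it, and declare the departure in SAP 5.4.

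Either change is a matter of wording and programming specification and needs no new data. The first costs almost nothing if made before the tables are programmed; the second adds one summary table.

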15. STUDY MEDICATION EXPOSURE

The duration of exposure in days will be calculated as follows:

Duration of exposure in days =

date of last study treatment administration – date of first study treatment administration + 1.

The dates of first and last study treatment administration will be taken from the IP eCRF. Interruptions, compliance, and dose changes are not considered for duration of exposure. Exposure to study medication in days will be summarized for the SAF.

16. STUDY MEDICATION COMPLIANCE

Compliance with the study treatment will be presented for the SAF and calculated based on the total volume administered as captured on the IP eCRF. The 750mg IV loading dose of ANB019-002 is administered on Day 1 following dilution by the site pharmacist to a total volume of 100 ml with 0.9% sodium chloride.

Subject compliance to the loading dose will be calculated based on the total volume administered (e.g. 95 or 110 ml) as a percentage of the prescribed volume for that dose (100 ml). This will only be based on the volume injected, as the volume of ANB019 that has been diluted, is not captured.

The 3 follow-up doses of ANB019-002 are administered SC, 100 mg each in a 1 ml solution that is prepared by the IP manufacturer and provided in glass vials. Subject compliance to the follow-up doses will be calculated based on the total volume administered (e.g. 0.9 ml) as a percentage of the prescribed volume for that dose (1 ml). As the solution is prepared by the manufacturer, it is assumed that treatment administration will not exceed 1 ml. Overall compliance for a subject will not be calculated.

Compliance with the IV loading dose will be calculated as follows:

Compliance with IV loading dose = Total ml administered / 100 ml x 100

Compliance with each of the three SC follow-up doses will be calculated as follows:

Compliance with SC follow-up dose = Total ml administered / 1 ml x 100

17. EFFICACY OUTCOMES

17.1. PRIMARY EFFICACY

17.1.1. RESPONSE BASED ON CLINICAL GLOBAL IMPRESSION SCALE

The primary efficacy endpoint is the proportion of subjects achieving clinical response at Weeks 4 and 16. The clinical response is defined as a composite score which considers both the CGI and reduction in the mJDA score (compared to Baseline) at that visit, and is classified as "Very much improved", "Much improved", or "Minimally improved" on the 5-point CGI scale (see **Table C. Clinical Global** Impression).

Page 10 of 43

Table C. Clinical Global Impression

Change in mJDA Severity Index Total score	and/ or	CGI Category description	CGI scale and Responder status
Reduction by 3 or >3 points	or	Clear or almost clear of signs of GPP	Very much improved
			Responder
Reduction by 1 or 2 points	or	At least one of the following: Area of erythema with pustules (%) reduced by ≤30%, or Clinically meaningful improvement in at least two other components of the mJDA severity index for GPP (area of erythema, area of edema, fever, white blood cells (WBC), C-reactive protein (CRP) and serum albumin (Alb)).	Much improved Responder
0 points (no change)	and	At least one of the following: Area of erythema with pustules (%) reduced by ≤20%, or Clinically meaningful improvement in at least one other component of the mJDA severity index for GPP (area of erythema, area of edema, fever, WBC, CRP, Alb)	Minimally improved Responder
0 points (no change)	and	Not meeting the CGI criteria of "minimally improved"	No change Non- responder
Increased $\geq + 1$ point		Not applicable	Worsened Non- responder

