### **6.5.1 Rescue Medicine**

Rescue medication will be directed by the Investigator as needed. Rescue medication in the form of topical corticosteroids (eg, betamethasone valerate ointment and cream, mometasone furoate ointment and cream) can be used during the study for a period of up to 1 week on a daily basis on affected areas to provide symptomatic relief. The introduction of any rescue medication must be communicated and discussed with the Medical Monitor. Rescue medication will be provided by the site and reimbursed by the Sponsor.

The use of rescue medications should be delayed, if possible, for at least 1 month following the administration of study treatment. Rescue medication may be used at the Investigator's discretion only if medically indicated for the wellbeing of the subject. The date and time of rescue medication administration as well as the name and dosage regimen of the rescue medication must be recorded.

The addition of any systemic psoriasis medication that is likely to impact psoriasis signs and symptoms (eg, cyclosporine, methotrexate, and retinoid) will require the subject to be withdrawn from the study.

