**Table 3 Analysis Sets**

Full Analysis Set (FAS)	The FAS analysis set will include all subjects, regardless of whether or not the treatment was received. Subjects will be analyzed according to treatment received.
Safety Analysis Set	The Safety Analysis Set will include all enrolled subjects who receive at least 1 dose of ANB019. The Safety Analysis Set will be used for all safety analyses. Subjects will be analyzed according to treatment received.
Per Protocol Analysis Set (PPS)	The Per Protocol analysis set will include all subjects in the FAS analysis set who do not have major protocol violations that would affect the evaluation of the primary efficacy endpoint.
PK Analysis Set	The PK analysis set will include all subjects in the Safety Analysis Set who have at least 1 quantifiable PK sample available and who do not have events or deviations with the potential to affect PK concentrations. The PK analysis set will be used for all PK analyses.

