17.1.3. ANALYSIS OF PRIMARY EFFICACY VARIABLE

This is an exploratory study and no formal hypothesis testing will be performed. The primary efficacy analysis will be performed on the FAS (see Section 8). Descriptive summary statistics will be presented for the CGI. The number and proportion of subjects achieving clinical response will be summarized in tabular form for Weeks 4 and 16. Each subject's CGI category will be plotted over all study visits.

The proportion of subjects having a clinical response at Weeks 4 and 16 will be derived using all subjects randomized and enrolled as the denominator for this calculation.

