17.1.4. SENSITIVITY ANALYSIS OF PRIMARY EFFICACY VARIABLE(S)

There will be no sensitivity analysis for this exploratory study.

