17.2.3. ANALYSIS OF SECONDARY EFFICACY VARIABLES

All secondary efficacy analysis will be performed on the FAS (see Section 8).

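### The primary response rate takes no account of permitted rescue, so a rescued subject can be reported as an ANB019 responder, and no planned analysis shows the rate without such subjects

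*SAP*

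**What the plan says.** **Response.** SAP 17.1.1 (Table C) and Protocol 9.4.4.1 with Appendix 8 class a subject from the CGI category and the change in mJDA total score. The SAP calls this a composite that "considers both the CGI and reduction in the mJDA score (compared to Baseline) at that visit". The lowest responder category, *Minimally improved*, needs no change in mJDA points. A small fall in the area of erythema with pustules, or a meaningful improvement in one other component, is enough.

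**Rescue.** Under Protocol 6.5.1, topical corticosteroids "can be used during the study for a period of up to 1 week on a daily basis on affected areas". On timing it says: "The use of rescue medications should be delayed, if possible, for at least 1 month following the administration of study treatment". It requires withdrawal only when a systemic psoriasis medication is added.

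**Non-response at Week 4.** SAP 5.1 and 17.1.2 and Protocol 4.1 terminate subjects rated *No change* or *Worsened* at Week 4. SAP 17.1.2 keeps them as non-responders at Week 16.

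**Analysis.** SAP 17.1.3 uses the FAS, with the proportion "derived using all subjects randomized and enrolled as the denominator for this calculation". SAP 17.1.4 adds: "There will be no sensitivity analysis for this exploratory study". SAP 17.2.3 states: "All secondary efficacy analysis will be performed on the FAS". SAP 9.4 excludes subgroup analyses. SAP 14 lists rescue medication and summarizes it by ATC class, without linking it to response.

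**The concern.** The study is single-arm and open-label, so the responder proportion is its main efficacy result and is read as the effect of ANB019. If a subject's affected skin was treated with topical corticosteroid before a rating, the improvement may not be due to ANB019 alone. The protocol itself treats this class as able to disturb the assessment: topical corticosteroids need a 2-week washout before baseline (Protocol 5.2 and Table 6). Even bland emollients are barred in the 24 hours before a visit (Protocol 6.5), yet 6.5.1 sets no interval between rescue and an efficacy visit.

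What is at stake is interpretation, not error rates, because no hypothesis is tested. The same proportion also enters the interim analysis, which may guide protocol changes and later studies (Protocol 9.5).

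**Working it through.** The plan has no figure to reproduce: the sample size of about 10 is stated as not based on power (SAP 5.2). The check is mainly of the text, with arithmetic for scale.

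**1. Can a rescued subject be a responder?** Sections 17.1.1 to 17.1.4 of the SAP do not mention rescue. Protocol 6.5.1 keeps the subject in the study after topical rescue. The rating at the next visit then decides the status, and *Minimally improved* can be met by a change in the treated skin. So yes.

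**2. Does any other output separate such subjects?** Sensitivity and subgroup analyses are excluded. Primary and secondary efficacy both use the FAS. The per-protocol set keeps FAS subjects "who do not have major protocol violations that would affect the evaluation of the primary efficacy endpoint", but no efficacy analysis is assigned to it. So no.

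**3. When could rescue matter?** Taking 1 month as 28 to 31 days:
- If the delay follows the Day 1 dose, it ends at Day 1 + 28 to 31 = Day 29 to 32. Days 29–112 (84 days) or Days 32–112 (81 days) before the Week 16 visit on Day 113 are then outside the delay.
- If it follows every dose (Days 1, 29, 57 and 85), it runs to Day 85 + 28 to 31 = Day 113 to 116. Rescue before Week 16 then arises only where delay is not possible.

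Protocol 6.5.1 does not say which dose is meant. These are days of opportunity, not a rate of use. Rescue before Week 4 is discouraged on both readings and excluded on neither.

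**4. What can rescue after Week 4 change?** A subject rated a non-responder at Week 4 leaves the study and is fixed as a non-responder at Week 16. For anyone rated at Week 4, later rescue can therefore only sustain or restore a response already recorded.

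**5. Size.** With x responders among n = 10, the rate is x/10, and one recoded subject moves it by 1/10 = 10 points. The exact (Clopper-Pearson) 95% limits are the 0.025 quantile of Beta(x, n − x + 1) and the 0.975 quantile of Beta(x + 1, n − x). Starting from an assumed 8 responders:

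| Rescued responders | Rate counting them as non-responders | Exact 95% CI |
|---|---|---|
| 0 | 8/10 = 80% | 44.4 to 97.5% |
| 1 | 7/10 = 70% | 34.8 to 93.3% |
| 2 | 6/10 = 60% | 26.2 to 87.8% |
| 3 | 5/10 = 50% | 18.7 to 81.3% |

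**6. Could it happen at all with 10 subjects?** If each subject has probability q of using rescue, independently, the chance of at least one rescued subject is 1 − (1 − q)^10. For assumed q of 5%, 10%, 20% and 30% this is 40.1%, 65.1%, 89.3% and 97.2%. A rescued subject is not necessarily a rescued responder, so these are upper limits for the event of interest.

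**The case against.** **The Week 4 rule protects Week 16.** This largely stands. A reader might infer that rescue can turn ANB019 failures into Week 16 responders. For subjects rated non-responders at Week 4 the documents exclude that. What remains is a relapse after Week 4 that rescue hides by Week 16, and the less likely case of rescue before Week 4.

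**Rescue may be a violation or lead to withdrawal.** Appendix 5 prohibits therapy likely to work in GPP or psoriasis, calls use of an excluded medication a protocol violation, and provides for withdrawal if a prohibited treatment is essential. Table 6 names topical corticosteroid. If a subject were withdrawn on that basis before Week 16, the status would stay missing within the all-enrolled denominator, so the subject would not count as a responder. This stands as an uncertainty: Protocol 6.5.1 and Appendix 5 conflict, and major or minor status is settled only in deviation review. It does not close the gap, since the response definition still ignores rescue and no per-protocol response rate is planned.

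**Response regardless of rescue is a legitimate choice in a descriptive study.** This stands. The protocol defines the endpoint without rescue, SAP 5.4 declares no change from the protocol, and SAP 1 notes that changing planned variables may require a protocol amendment. A reader might infer that the headline must be recoded; the documents do not support that.

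**The data are already visible.** Rescue dates and times are recorded, data are listed by subject and each subject's CGI is plotted. With about 10 subjects, cross-matching is easy. That lowers the stakes, but matching by hand after the fact is not a prespecified rate.

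**Conclusion.** The gap is real but narrow. As planned, the response rate can include subjects whose rating followed topical corticosteroid, and no planned analysis shows the rate without them. At Week 16 the problem is mainly masked relapse. At Week 4 it depends on rescue that the protocol discourages but does not exclude.

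The size is about 10 points per rescued responder, assuming about 10 enrolled subjects. The number of such subjects is unknown. The 8/10 starting rate, the counts of 1 to 3 and the rescue probabilities are assumptions. A reader might infer that the reported rate will be inflated; the documents do not support this, because with no rescued responders the two rates are the same. Nor do they settle whether permitted rescue is a protocol violation. This is a cheap improvement in reporting, not a flaw that undermines the study.

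**What to change.** 1. **SAP 17.1.3:** keep the protocol-defined proportion as the headline and state that it is regardless of rescue.
2. **SAP 17.1.4:** replace the exclusion of sensitivity analysis with one prespecified supplementary row at Week 4 and at Week 16. Count as a non-responder any subject who started rescue, or another GPP or psoriasis therapy, after the Day 1 dose and before that assessment, identified by recorded dates. Bland emollients and therapy started before Day 1 do not count. Report both proportions with exact 95% CIs; Protocol 9.4 asks for two-sided 95% intervals where applicable.
3. **Protocol:** the sponsor must reconcile 6.5.1 with Appendix 5 and Table 6, and clarify which dose the 1-month delay refers to.

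Items 1 and 2 cost a few SAP sentences and one table row. Protocol 9.4.9 leaves sensitivity analysis to the SAP, the dates are already collected, and the endpoint definition is unchanged. The downside is that the supplementary rate may be lower, and a brief early rescue counts as failure at Week 16. Showing both rates lets the reader see how much that matters. Item 3 needs a protocol clarification.
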